9.3.2.2 Secondary Outcomes

9.3.2.2.1 Pregnancy Outcomes

- Rate of spontaneous abortion where spontaneous abortion is defined as non-deliberate fetal death which occurs prior to 19 completed weeks post-LMP
- Rate of elective abortion where elective abortion is defined as deliberate termination of pregnancy at any time in gestation
- Rate of stillbirth where stillbirth is defined as non-deliberate fetal death anytime in gestation at or after 19 completed weeks post-LMP
- Rate of premature delivery where premature delivery is defined as live birth prior to 37.0 weeks gestation as counted from LMP (or ultrasound adjusted date)

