9.5 Study Size

An enrollment total of 75 in the exposed group and 150 in each of the 2 comparison groups after 10 years is anticipated. Given that these numbers assume the prevalence of exposure is sufficient to support recruitment of these numbers, the feasibility of achievement will be re-evaluated at each annual interim review of the data.

Based on previous experience with MotherToBaby/OTIS Pregnancy Studies, we estimate that subjects will be an average of 7-10 weeks post-LMP at the time of enrollment. Given this mean gestational timing at enrollment, the anticipated spontaneous abortion/stillbirth rate is 10%, the estimated elective abortion rate is 5%, and the estimated lost to follow-up rate is 5%. This results in an estimated 71 observable pregnancies of which 60 are estimated to result in live births in cohort 1 (exposed group), and an estimated 142 observable pregnancies of which 120 are estimated to result in live births in cohorts 2 and 3 (control groups).

Baseline rates of major structural **birth** defects, spontaneous abortion, premature delivery, and small for gestational age, as well as the standard deviation for mean birth weight of full-term infants were based on previous MotherToBaby/OTIS studies and on general population data (Table 3). With the sample size estimated above, at $\geq 80\%$ power, alpha of 0.05, two-tailed tests of significance (except as noted below for pattern of minor structural **birth** defects), and each comparison group independently compared to the exposed group, the minimum effect sizes detailed in Table 3 will be detectable.

With respect to the evaluation of minor malformations, the strength of this study design is in the ability to examine the data for a pattern of minor and/or major structural **birth** defects, given that the known human teratogens are typically associated with a pattern as opposed to isolated major **structural** birth defects. A baseline prevalence estimate of 1% has been used for a specific pattern of minor **structural birth** defects. The RR detectable with this sample size is 10.0. This represents a 10% birth prevalence of a specific pattern (ie, approximately 6 children in the exposed sample), which is comparable to the birth prevalence of a specific pattern in other known human teratogens of moderate risk such as the anticonvulsant medications.

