9.7.2.4.1 Description of Study Enrollment

Outcome	Analysis Subset
Major Structural Birth Defect Among Live Births	All pregnancies ending in at least 1 live born infant
Major Structural Birth Defects Among All Pregnancies Excluding Lost to Follow-Up	All pregnancies excluding lost to follow-up
Spontaneous Abortion	Pregnancies enrolled prior to 20 weeks' gestation
Stillbirth	Pregnancies enrolled excluding lost to follow-up
Preterm Delivery	Pregnancies enrolled prior to 37 completed weeks' gestation, excluding pregnancies ending in twin or higher order multiple births
Minor Structural Birth Defects	Live born infants who have received the dysmorphology examination
Small for Gestational Age Infants	Live born infants excluding twin or higher order multiple births
Breastfeeding	Pregnancies ending in at least 1 live born infant
Postnatal Growth	Live born infants followed up to 1 year postpartum, excluding twin or higher order multiple births
Serious or Opportunistic Infections	Live born infants followed up to 1 year postpartum
Immune Function	Live born infants who received the tetanus titer testing
Response to vaccines	Live born infants who received at least one vaccine
Neurodevelopment	Live born infants for whom developmental screening questionnaires were completed or face-to-face testing was completed

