9.7.2.5.2 Secondary Analysis

The following will comprise the secondary analyses:

1. Comparison of all secondary outcomes between the Specific Evolocumab-Exposed cohort and Comparison Group I
2. Comparison of the primary and all secondary outcomes between the Specific Evolocumab-Exposed cohort and Comparison Group II

The comparison of the prevalence of the total proportion of major structural **birth** defects between the Specific Evolocumab-Exposed cohort and Comparison Group II will be among all live births and, separately, among all pregnancies excluding those lost to follow-up. The comparison of the prevalence of ≥ 3 minor malformations between the Specific Evolocumab-Exposed cohort and each of the 2 comparison groups will be among children who receive the dysmorphological examination. The comparison of IgG-tetanus antibody status (test negative or indeterminate vs test positive) by group (Exposed, Comparison Group I, Comparison Group II) among those in the biological sample sub-study.

In each cohort we will separately calculate the proportion of all pregnancies ending in live birth, spontaneous abortion, stillbirth, elective termination, and lost to follow-up; crude comparisons will be made between cohorts.

The evaluation for a pattern of minor structural **birth** defects will be conducted using the following steps:

1. A comparison among groups of the proportion of infants with any 3 or more minor structural **birth** defects will be made without regard to pattern
2. Among infants with 3 or more minor **structural birth** defects, the Evolocumab-Exposed group will be examined for evidence of a specific pattern of 3 or more defects in any 2 or more children. If such a pattern is identified, Comparison Groups I and II will be evaluated for any evidence of the same pattern.

In each cohort among all live born infants we will separately calculate the proportion of premature delivery, small for gestational age on weight, length or head circumference, and rates of serious infections, hospitalizations, adverse vaccine reactions, and adverse neurodevelopmental outcomes; crude comparisons will be made between cohorts.

Mean birth weight, length and head circumference for full-term live born infants will be compared between cohorts. Postnatal growth parameters will be compared using the proportion of infants ≤ 10 th centile for sex and age with respect to weight, height, or head circumference.

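### The protocol fixes two conflicting denominators for preterm delivery, and the one in the analysis-subset table counts pregnancies that can never be a preterm live birth

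*Protocol*

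**What the plan says.** Four places in the protocol bear on the preterm denominator.

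- **Definition (9.3.2.2.1):** "premature delivery is defined as live birth prior to 37.0 weeks gestation as counted from LMP". A spontaneous abortion, elective abortion or stillbirth cannot be an event.
- **Analysis-subset table (9.7.2.4.1), Preterm Delivery row:** "Pregnancies enrolled prior to 37 completed weeks' gestation, excluding pregnancies ending in twin or higher order multiple births". This filters on enrollment week and on multiples. It does not require a live birth and does not remove losses to follow-up. Other rows of the same table do apply such filters: small for gestational age is limited to live born infants, and the stillbirth row excludes losses to follow-up.
- **Secondary analysis (9.7.2.5.2):** "In each cohort among all live born infants we will separately calculate the proportion of premature delivery". This requires a live birth but sets no singleton or enrollment-week condition.
- **Study size (9.5 and Table 3):** preterm delivery is powered on 60 v 120, the live-birth counts derived in 9.5, with a 9% baseline, a relative risk of 2.8 and a stated power of 85%.

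**The concern.** Preterm delivery is a secondary outcome with its own power row, and estimating rates is the stated secondary objective (8.2). On the table's denominator, the preterm proportion falls mechanically as fetal loss or termination rises, because those pregnancies stay below the line and can never appear above it. The absolute rate is then too low in every cohort. If loss or termination differs between cohorts, the relative risk is also multiplied by the ratio of the live-birth fractions. In a safety registry that direction is unwelcome: more fetal loss in exposed women would pull the preterm comparison toward or below 1. The protocol gives reasons not to assume equal fractions. It powers for a fetal-loss relative risk of 2.5 (Table 3), and it expects some exposures in unintended pregnancies, with possible imbalance between groups (9.9).

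The alternative set in 9.7.2.5.2 is not quite clean either. It keeps multiples, and it keeps infants of women enrolled at or after 37 weeks, who cannot be preterm.

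**Working it through.** **Inputs (9.5 and Table 3).** Enrolled: 75 exposed, 150 per comparison group. Lost to follow-up 5%, spontaneous abortion/stillbirth 10%, elective abortion 5%. Preterm baseline 9%, relative risk 2.8, so 0.09 × 2.8 = 25.2% in the exposed.

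**Step 1: the protocol's own counts.** 75 × 0.95 = 71.25 and 150 × 0.95 = 142.5, stated as 71 and 142. 71 × 0.85 = 60.35 and 142 × 0.85 = 120.7, stated as 60 and 120. These reproduce, and they show that Table 3's 60/120 are live births. The stated 85% power is not reproduced: the pooled two-sided formula gives 80.5%, and exact enumeration of the uncorrected chi-square test gives 81.6%. Nothing below depends on the 85%.

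**Step 2: absolute rate under the table row.** Rate = 9% × (live births ÷ denominator).

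- Lost to follow-up left out: 9% × 60/71 = 7.6%, which is 15.5% too low.
- Lost to follow-up kept in: 9% × 60/75 = 7.2%, which is 20% too low.

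**Step 3: relative risk.** Apparent RR = true RR × (exposed live-birth fraction ÷ comparison live-birth fraction).

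With equal fractions the factor is 1, so 2.8 stays 2.8. Exact chi-square power hardly moves: 80.5% on 71/142 (25.2% × 0.85 v 9% × 0.85), against 81.6% on 60/120.

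For unequal fractions, hold elective abortion at 5% in both cohorts, fetal loss at 10% in the comparison group, and the preterm rate at 9% among live births in both:

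| Fetal-loss RR | Exposed live-birth fraction | Comparison | Null preterm RR reads |
|---|---|---|---|
| 1.5 | 0.80 | 0.85 | 0.94 |
| 2.0 | 0.75 | 0.85 | 0.88 |
| 2.5 | 0.70 | 0.85 | 0.82 |

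At a fetal-loss RR of 2.5, a true preterm RR of 2.8 reads 2.8 × 0.70/0.85 = 2.31.

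**Step 4: power in that last scenario (exact enumeration, uncorrected two-sided chi-square).**

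- Table row: 71 v 142, with 25.2% × 0.70 = 17.6% v 9% × 0.85 = 7.65%, gives 58%.
- Live births: 71 × 0.70 ≈ 50 v 142 × 0.85 ≈ 121, with 25.2% v 9%, gives 78%.

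**The case against.** The strongest reply is that the passages can be read together: the table supplies the enrollment and singleton filters, and 9.7.2.5.2 and the definition supply the live-birth filter. The table also sits under the descriptive-analysis heading, while 9.7.2.5.2 governs the comparison. This stands to the extent that dilution is not certain; it occurs only if the table row is applied as written. It does not remove the conflict, because nothing in the protocol says that the two are to be combined.

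The 7.2% figure needs pregnancies of unknown outcome to be counted as not preterm. Section 9.7.2.3 treats their outcome as unobtainable, 9.9 plans no imputation, and the row's exclusion by type of ending presupposes a known ending. So 7.6% is the likelier figure.

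The enrollment-week condition would suit a time-to-event risk set with losses censored, and 9.7.2.5.2 names Cox models where appropriate. But it does not assign them to preterm delivery, and its first comparison is a crude proportion.

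The masking scenario is a chosen one. With about 4.5 events among 71 v 10.9 among 142, an apparent RR of 0.82 has a 95% interval of roughly 0.28 to 2.4, so it would not pass for evidence of protection. The excess loss would also be visible, since fetal loss is itself a powered comparison. Late enrollment matters little when average enrollment is expected at 7 to 10 weeks.

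A reader might infer that the stillbirth row, "Pregnancies enrolled excluding lost to follow-up", has the same fault, because stillbirth requires reaching 19 completed weeks. The documents do not support calling it an error. Section 9.7.2.5.2 reports "the proportion of all pregnancies ending in live birth, spontaneous abortion, stillbirth, elective termination, and lost to follow-up", and a stillbirth proportion per pregnancy is a coherent part of that distribution. The risk among pregnancies reaching 19 weeks would be higher, with the per-pregnancy figure some 10 to 15% lower on assumed splits that the protocol does not give, but that is a different measure.

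**Conclusion.** The finding is a contradiction between two sections on the preterm denominator. If the table row is followed, the absolute rate reads 7.6% instead of 9%, or 7.2% on the less likely reading that keeps pregnancies lost to follow-up. These sizes rest on the attrition rates in 9.5.

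Bias in the relative risk is conditional. There is none at equal live-birth fractions, and the factor is 0.82 at 25% v 10% fetal loss. That benchmark assumes equal elective abortion in both cohorts and preterm risk among live births that is unrelated to the excess loss.

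Two stronger inferences should be avoided. The protocol does not commit the study to a diluted rate, and it does not make a harmful drug look protective as a matter of course. Nor is Table 3 a third denominator: its 60/120 are the live births of 9.5.

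The point is worth correcting because the outcome is powered, the texts conflict, and the denominator should not be chosen after the data are seen.

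**What to change.** Use one preterm set in both the 9.7.2.4.1 table row and 9.7.2.5.2: live-born singletons from pregnancies enrolled before 37 completed weeks, excluding lost to follow-up. This changes one table row and one sentence. It needs no new data, since pregnancy dating, date of delivery and type of outcome are already collected (9.3.1, 9.4.3).

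The set will be slightly smaller than Table 3's 60/120, which makes no deduction for multiples, and a note to Table 3 should say so. The stillbirth row needs no correction.

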- Principal Investigator: PPD [REDACTED], PhD, MPH

Department of Pediatrics

Center for Better Beginnings

University of California San Diego

[name]

Phone: PPD [REDACTED]

Email: PPD [REDACTED]

4. Abstract

- Study Title: Evolocumab Pregnancy Exposure Registry: An OTIS Pregnancy Surveillance Study
- Study Background, Rationale, and Design

In the United States (US), evolocumab is indicated:

(1) In adults with established cardiovascular disease to reduce the risk of myocardial infarction, stroke, and coronary revascularization; (2) As an adjunct to diet, alone or in combination with other lipid-lowering therapies (eg, statins, ezetimibe), for the treatment of adults with primary hyperlipidemia (including heterozygous familial hypercholesterolemia) to reduce low-density lipoprotein cholesterol (LDL-C); and (3) As an adjunct to diet and other LDL-lowering therapies (eg, statins, ezetimibe, LDL apheresis) for the treatment of patients with homozygous familial hypercholesterolemia (HoFH) who require additional lowering of LDL-C (revised United States Prescribing Information [USPI], December 2017). There are no data available on use of evolocumab in pregnant women to inform a drug-associated risk. In Section 8.1, the USPI for evolocumab states to “consider the benefits and risks of REPATHA and possible risks to the fetus before prescribing REPATHA to pregnant women”. **Information on the pregnancy exposure registry was added to Section 8.1 of the USPI as well as to the US Patient Package Insert (December 2017).**

This study is being conducted to address a requirement by the Food and Drug Administration (FDA) to conduct a prospective observational study of pregnant women exposed to evolocumab to evaluate fetal, infant, and childhood outcomes of pregnant women exposed to evolocumab and their live born offspring through the first 5 years of life to estimate incidence rates for the potential safety signals of adverse pregnancy outcomes, embryo-fetal growth and development, and adverse infant and childhood outcomes related to humoral immune suppression.

- Research Question and Objective(s)

- Primary Objective(s)

- To estimate the overall combined rate of major structural **birth** defects, as well as to evaluate any pattern of anomalies, in infants of women with ASCVD, or **hypercholesterolemia associated with** familial hypercholesterolemia (FH) exposed to evolocumab during pregnancy.

- Secondary Objective(s)

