- Rate of stillbirth, defined as non-deliberate fetal death anytime in gestation at or after 19 completed weeks post-LMP
- Rate of premature delivery, defined as live birth prior to < 37 completed weeks gestation as counted from LMP
- Infant Outcomes
 - Rate and pattern of > 3 minor structural **birth** defects, where a minor structural **birth** defect is defined as a structural anomaly which has neither cosmetic nor functional significance to the child (itemized on the study examination form), and a pattern is defined as the same 3 or more minor malformations in 2 or more children
 - Rate of small for gestational age, defined as birth size (weight, length, or head circumference) < 10th centile for sex and gestational age using standard pediatric CDC growth curves for full term or preterm infants
 - Rate of postnatal growth deficiency, defined as postnatal size (weight, length, or head circumference) < 10th centile for sex and age using standard pediatric growth curves, and adjusted for postnatal age for premature infants if the postnatal measurement is obtained at < 1 year of age
 - Rate of postnatal serious infections and hospitalizations, as assessed throughout the 5-year postnatal follow-up period via pediatric records
 - Rate of infant reactions to scheduled vaccinations, as assessed throughout the 5-year postnatal follow-up period via pediatric records and a questionnaire designed to collect this information
 - Adequacy of immune response, as defined by an immunoglobulin (Ig)G-tetanus antibody assessment performed in the child between 6-12 months of age
 - Rate of adverse neurodevelopmental outcomes, as assessed in the child during 2 periods (between 16 months and 17 months 30 days of age and between 3.5-5 years of age) via standardized tests of performance
- Breastfeeding/Lactation Outcomes
 - Proportion of women who report breastfeeding (at all) in the first 6 weeks post-delivery; among women who breastfed in the first 6 weeks post-delivery, the proportion who breastfed exclusively for 2 weeks (both assessed via questionnaire administered between 0 – 6 weeks post-partum)

Exposure Variable(s)

The period defining exposure to evolocumab during pregnancy will be any number of days, at any dose, and at any time from the first day of the LMP up to and including the end of pregnancy. The period defining non-exposure to evolocumab during pregnancy will be no exposure any time within 90 days prior to the first day of the LMP.

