9.3.2.2.2 Infant Outcomes

- Rate and pattern of minor structural **birth** defects where a minor structural **birth** defect is defined as a structural anomaly (itemized on the study examination form) which has neither cosmetic nor functional significance to the child, and a pattern is defined as the same 3 or more minor structural **birth** defects in 2 or more children (see [Appendix A](#), 04.E. Dymorphology Exam Form). Due to the large variability in the sensitivity and specificity of identification of minor defects, in this study, minor defects are tabulated only in those infants who receive the study-related physical examination. This approach of assessment for clusters is based on prior studies that suggest 3 or more minor malformations is a meaningful cut point ([Leppig et al, 1987](#); [Méhes et al, 1973](#); [Marden et al, 1964](#)).
- Rate of small for gestational age where small for gestational age is defined as birth size (weight, length, or head circumference) \leq 10th centile for sex and gestational age using standard pediatric CDC growth curves for full term or preterm infants ([NCHS, 2000](#); [Olsen et al, 2010](#)).
- Rate of postnatal growth deficiency where postnatal growth deficiency is defined as postnatal size (weight, length, or head circumference) \leq 10th centile for sex and age using standard pediatric growth curves, and adjusted for postnatal age for premature infants if the postnatal measurement is obtained at less than 1 year of age.
- Rate of postnatal serious infections (see [Appendix D](#)) and hospitalizations as assessed throughout the 5-year postnatal follow-up period. Pediatric records will be requested after delivery and then on an annual basis with specific requests for documentation of serious infections and hospitalizations
- Rate of infant reactions to scheduled vaccinations as assessed throughout the 5-year postnatal follow-up period. Pediatric records and a questionnaire regarding vaccine administration according to recommended schedule and any vaccine-related adverse events will be obtained on an annual basis (see [Appendix A](#), 08.12. Vaccine Information Form).
- Infant response to IgG-tetanus antibody as a biological marker to evaluate humoral immune response. To be performed via a heel stick **or venipuncture** and standardized assay test between 6-12 months of age in a subset of infants in each of the study groups, conditional on the consent of the mother.

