9.4.4 Medical Records, Pediatric Evaluations

Upon completion of the outcome interview, each woman will be mailed a packet containing medical records release forms for the delivery hospital, obstetrician (**if the release form has not been received**), pediatrician, internist, cardiologist or other specialty physician if applicable (see [Appendix A](#), Form 09.J. Sample OB Medical Records Release Form). For women whose pregnancies have ended in spontaneous or elective abortion or stillbirth, records release forms will be mailed for the specialty physician's evaluation, if applicable, and if prenatal diagnosis, pathology or autopsy reports are available. Each woman will be asked to sign the forms and to return them along with the **patient** exposure diary. Specific information on maternal cholesterol levels obtained prior to and during pregnancy will be requested for women in the Evolocumab-Exposed group and Comparison Group I.

Upon receipt of the signed medical records release forms, a standard physical evaluation form (see [Appendix A](#), 06.H. Birth Info and Private Pediatrician Form) will be mailed to each pediatrician or other physician responsible for the care of each live born infant. This form includes information on infant size at the time of the latest examination and questions about postnatal complications and congenital anomalies. After delivery, at 1 year of age, and annually thereafter until the child's fifth birthday, a medical records release form for the pediatrician or health care provider caring for the child will be sent to the mother for signature. The signed form along with a standard questionnaire about infant/child growth, congenital malformations, serious infections (see [Appendix D](#) for list of conditions qualifying as serious infection), hospitalizations, and adverse reactions to vaccinations administered is sent to the health care provider (see [Appendix A](#), 07.I. Pediatric One Year Follow-up Form, and 08.I2. Vaccine Information Form).

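### Serious infections are defined and collected over 5 years, but their analysis subset refers to 1 year and no section says how years 2 to 5 are analysed

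*Protocol*

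**What the plan says.** The Abstract (Section 4) lists the endpoint as "Rate of postnatal serious infections and hospitalizations, as assessed throughout the 5-year postnatal follow-up period via pediatric records". Section 9.3.2.2.2 repeats it: "hospitalizations as assessed throughout the 5-year postnatal follow-up period". The FDA requirement described in Sections 4 and 7 covers exposed women and "their live born offspring through the first 5 years of life", and names infant and childhood outcomes related to humoral immune suppression.

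Data collection matches that window. Under Section 9.4.4 the release form and the questionnaire that covers serious infections and hospitalizations go out after delivery, "at 1 year of age, and annually thereafter until the" fifth birthday. Section 9.4.7 describes this 5-year information as covering all live born children in the study.

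Two statements govern the analysis:

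- Section 9.7.2.4.1, row for serious or opportunistic infections: "Live born infants followed up to 1 year postpartum".
- Section 9.7.2.5.2, a single sentence that opens with "In each cohort among all live born infants we will separately calculate the proportion of premature delivery" and ends "and rates of serious infections, hospitalizations, adverse vaccine reactions, and adverse neurodevelopmental outcomes; crude comparisons will be made between cohorts". It sets no time limit.

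Hospitalizations share the 5-year definition but have no row in the subset table.

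**The concern.** Serious infection is the clinical outcome closest to the humoral immune suppression that the protocol reports for another drug of the class in infant monkeys. The protocol fixes a subset for this outcome that fits neither its own definition nor its own analysis text, and it does not say what happens to infections in years 2 to 5. It does deal with that question for birth defects: Section 9.3.2.1 says that defects found after 12 months and up to 5 years are described separately.

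An analyst who follows the row literally could stop counting at 12 months, or could keep only infants with a completed first year. The first choice leaves collected data unused. The second conditions the infection analysis on surviving and staying under observation for a year, although Appendix D lists neonatal sepsis among the qualifying infections. If the window is left open, it can also be chosen after the data have been seen.

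**Working it through.** The protocol states no sample size, power or baseline rate for serious infections, and Table 3 has no such row. There is therefore no planned figure to reproduce. The check compares the texts and then counts child-time.

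**Texts side by side**

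| Place | Who | Window |
|---|---|---|
| Sections 4 and 9.3.2.2.2 | infants | 5 years |
| Sections 9.4.4 and 9.4.7 | all live born children | to age 5 |
| Section 9.7.2.4.1 | infants followed up to 1 year | not stated, or 1 year |
| Section 9.7.2.5.2 | all live born infants | none stated |

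**Child-years under the cut-off reading.** Section 9.5 expects 60 live births in the exposed cohort and 120 in each comparison cohort.

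- Exposed: 60 × 5 = 300 planned and 60 × 1 = 60 used, so 240 are unused.
- Each comparison group: 120 × 5 = 600 planned and 120 × 1 = 120 used, so 480 are unused.
- Share unused: 4/5 = 80%.

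**Allowance for the study end.** Section 9.2.1 gives a first enrollment in December 2016 and an end in October 2030. Section 9.2.2 gives 10 years of recruitment. Assume uniform enrollment and birth 0.58 years after enrollment.

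- A child enrolled at the end of year 10 is followed for 2030.83 − (2026.95 + 0.58) = 3.30 years.
- Follow-up is under 5 years if enrollment falls after 2030.83 − 5 − 0.58 = 2025.25, a share of (2026.95 − 2025.25)/10 = 17%.
- Mean follow-up is 5 − 0.17 × (5 − 3.30)/2 = about 4.86 years.
- Share unused: 1 − 1/4.86 = about 79%.

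Moving the gap between enrollment and birth from 0.5 to 0.65 years gives 290.6 to 292.1 exposed child-years in total. About 231 to 232 would then be unused in the exposed cohort, and twice that in each comparison group.

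**Precision under the cut-off reading.** The standard error of a log rate ratio is sqrt(1/d1 + 1/d0), where d1 and d0 are the event counts. If a share s of events is analysed in both groups, the standard error grows by 1/sqrt(s). The share is an assumption:

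- s = 0.20 (events spread evenly over 5 years): 1/sqrt(0.20) = 2.24.
- s = 0.40: 1/sqrt(0.40) = 1.58.
- s = 0.60: 1/sqrt(0.60) = 1.29.

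**Illustration with assumed risks.** Take 5% in year 1 and 2% in each later year. The 5-year risk is 1 − 0.95 × 0.98^4 = 12.4%. Expected exposed cases are 60 × 0.05 = 3.0 with one year of data and 60 × 0.124 = 7.4 with five. With 60 versus 120 children, two-sided alpha 0.05 and 80% power, the detectable relative risk is about 3.7 with one year of data and 2.4 with five. Neither risk comes from the protocol.

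**Under the other readings.** If the row only says which infants enter the denominator, no child-time after year 1 is lost among those infants and none of the widening applies. The question is then whether infants without a full first year are left out.

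**The case against.** The strongest reply is that the row defines a population and not a counting period. The column is headed as an analysis subset, other rows describe groups of pregnancies or infants, and the table sits under descriptive analysis. The text of Section 9.7.2.5.2 uses all live born infants without a 1-year limit. This much stands: a reader might infer that the plan discards most of the child follow-up, but that is one reading and not something the protocol states.

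A reader might also infer that infants who die in the first year are excluded. The row says up to 1 year, not at least 1 year, and no section excludes infant deaths. An infant who dies in month 4 could be counted as followed to its outcome. The exclusion is a possibility that the wording leaves open, no more.

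Nor does the row limit the whole immune question. Hospitalizations have no row, and Appendix D counts any infection leading to hospitalization as serious, so some later infections would still appear there. Vaccine reactions use infants with at least one vaccine, and the tetanus antibody test is placed at 6 to 12 months by design.

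Finally, unequal follow-up is not wholly ignored. Section 9.7.2.5.2 speaks of rates and allows Cox regression for adjusted comparisons where appropriate. The exact rate model, and any clustering for multiple births, properly belong in the SAP.

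What this reply leaves untouched is the contradiction. Even as a population, infants followed up to 1 year are not the same as all live born infants, and neither statement says how years 2 to 5 enter.

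**Conclusion.** The contradiction holds. A 5-year endpoint, with 5 years of records requested for every live born child, is paired with a subset row that refers to 1 year and with analysis text that has another denominator and no window.

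Under the cut-off reading, up to 80% of planned child-time goes unused: at most about 240 exposed child-years and 480 per comparison group, or about 79% with the October 2030 end under uniform enrollment. Under the completed-year reading, the possible harm is the exclusion of early deaths and losses, whose number the protocol does not allow one to estimate.

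The loss of precision cannot be stated, because there is no infection rate. The 1.3 to 2.2 times wider interval depends on 20% to 60% of events falling in year 1 and on the cut-off reading. This is a secondary outcome, but it answers a required safety question, so the row should be changed.

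**What to change.** In Section 9.7.2.4.1, define the subset for serious or opportunistic infections as all live born infants with any pediatric follow-up, with events counted from birth to death, last record or fifth birthday. Add hospitalizations to the same row. State the same denominator and window in Section 9.7.2.5.2, in line with Sections 4 and 9.3.2.2.2. Report year 1 as a named period within the 5 years.

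Use a method that allows for unequal follow-up, for example rates per child-year or the Cox model that Section 9.7.2.5.2 already permits. The details can be left to the SAP.

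The cost is one table row, a sentence of analysis text and slightly more analysis work. No new data are needed.
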